Study Design	This will be a single site, phase 2, safety and tolerability trial of 4'-phosphopantetheine (4'-PPT), a downstream product of intermediary metabolism in children and adults with pantothenate kinase-associated neurodegeneration (PKAN), an inborn error of vitamin B5 metabolism. There will be two cohorts: For the “ Primary Cohort ”, an initial 6-month, dose-ranging, parallel-group, randomized, double-blind, placebo-controlled phase will be followed by an 18-month, single-dose, open-label phase. During the double-blind phase, participants will be randomly assigned to receive one of three doses (5mg/m ² or 15mg/m ² or 20mg/m ²) or placebo in a 1:1:1:1 distribution. All participants will be assigned to a single dose (15mg/m ²) during the subsequent open-label phase. The primary data analysis will be based on the Primary Cohort dataset. Once the target enrollment of the Primary Cohort is met in the double-blind arm, new participants entering the study will be enrolled directly into an open-label arm that will last until the final subject in the Primary Cohort has completed their participation, including up to 4 additional mos for screening and follow-up. This will be designated the “ Open-label Cohort ”. Because the rolling enrollment into the Open-label Cohort will result in variable duration of participation, the safety and biomarker data from

	
the Open-label Cohort will not be used for the primary data analysis, although a secondary analysis of these data may be used for regulatory filings.
 
The study product will be taken once daily but may be split into divided doses if the participant does not tolerate a single daily dose.
 
Note that the double-blind phase of the study is not intended to be dose-finding: all doses are predicted to be many-fold below toxicity and all doses are predicted to correct the metabolic defect in PKAN, albeit with slightly differing time courses. The range of doses to be used during the double-blind phase is employed purely to test our hypotheses regarding the pharmacodynamic profile of an exploratory 'proof of concept' biomarker, CoASY. The mid-dose of 15mg/m² is based on the minimum effective dose in the mouse and converted to the human equivalent dose using an FDA algorithm and other guidances.

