Study Objective and Specific Aims	
The primary objective of this study is to evaluate safety and tolerability of the study product in adult and pediatric participants with PKAN.
 
The primary aims are:
 
• To compare safety or tolerability profiles of the study product between active and placebo groups over the 6-month double-blind parallel group phase of the study; and• To examine the long-term safety and tolerability profile of the compound over the 18-month (placebo group) -24-month (active group) active treatment period 
The primary hypothesis is that there will be no clinically significant difference in safety or tolerability profiles between active and placebo groups during six months of double-blind parallel study, nor between initial dose groups over 18-24 months of treatment with the study product.
 
The secondary aim is:
 
To evaluate the peripheral pharmacodynamic response of one component of a PKAN "molecular signature" (CoASY mRNA expression levels) in response to the study product.
 
The secondary hypotheses are that:
 
• CoASY mRNA expression levels will initially rise in all the study product-treated participants after 3 days ±2 days of treatment compared with placebo-treated participants; and• CoASY mRNA expression levels will subsequently decline in all participants after up to 18 months of study product treatment, consistent with secondary down-regulation of CoASY activity in the presence of excess substrate, (i.e. feedback inhibition); and

eIRB 18782 CoA-Z in PKAN (NIH)

	
There will be no difference in CoASY mRNA expression between initial treatment groups after up to 18 months of the single-dose active study product treatment. 
In a third exploratory aim, with the goal of informing future studies of the study product or other putative disease-modifying therapeutics, we will assess the feasibility of applying a latent growth curve (LGC) approach to natural history data collected before and during an intervention to detect disease-modifying effects.

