Sample Size Considerations	
Because PKAN is an ultra-rare disease, we are limited to 64 participants for the Primary Cohort (15 in each arm + 4 potential dropouts allowing for 5% loss to follow-up) whom we will recruit from our established research registry, (prioritizing those participating in our “PKANready” ongoing natural history study) as well as by methods described within the protocol. When our double-blind enrollment goal is met, enrollment of up to 86 additional participants will shift to an open-label arm, designated the Open-label Cohort. Our primary objective is to estimate effects of the study product and we will prioritize effect sizes over statistical power in interpreting results. Still, we wish to include sufficient numbers to estimate effects in our secondary and exploratory analyses of CoASY mRNA expression levels with some precision. In preliminary cross-sectional data, we found that the mean CoASY delta Ct (dCt) measures were 1.4 standard deviations higher in classic PKAN children (n=8) than age-matched healthy controls (n=6) on the log₂ scale, where higher dCt indicates lower CoASY activity (mean=17.39 vs 16.85, SD=0.39). We anticipate that participants at all three dose levels will resemble healthy controls after 3±2 days, while the placebo group will show no change. We simulated this change from baseline for 12 participants per group. For the standard deviation, we performed one set of simulations using the upper limit of the 60% CI for the standard deviation (0.34-0.48) as a conservative estimate. We regressed the dCt value on four indicator variables for study arm after treatment, with the intercept representing the common mean baseline value, and included a random intercept to induce correlation between paired measurements. We then used a Wald test for $\beta_{\text{placebo}1} - (\beta_{\text{low}1} + \beta_{\text{mid}1} + \beta_{\text{high}1})/3 = 0$ at $\alpha=0.05$. Pooling over 1000 simulated datasets, we find that we reject the null in 85-95% of simulations, approximating power to detect this difference at one month between the active and placebo groups.

-----------------------------------	---

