Statistical Methods	
A modified Intention-to-Treat (ITT) analysis dataset of all randomized participants who consumed at least one dose of the study product. This is also the Safety Analysis dataset.
 
The Per-Protocol dataset will include participants who consume at least 75% of assigned study product.
 
General approach
 
The proposed study takes place over 28 months in the Primary Cohort. A screening period of up to 2 months will be followed by an initial 6-month double-blind, placebo-controlled parallel trial of the study product during which participants will be assigned to one of three dose groups [5mg/m², 15mg/m², 20mg/m²]; and then by a further 18 months of open label study during which all participants will be assigned a 15mg/m² dose. Participants will be followed for up to two months beyond the end of the open-label period. The primary data analysis will be based on the Primary Cohort dataset.
 
Once the target enrollment in the Primary Cohort is met, we will shift to direct enrollment into an Open-label Cohort. A screening period of up to 2 months will be followed by up to 18 months during which all participants will be assigned a 15mg/m²

----------------------------	--

dose and follow a similar pattern of procedures as the Primary Cohort during the open-label phase of the study. Participants will be followed for up to two months beyond the end of their open-label period. Because the rolling enrollment into the Open-label Cohort will result in variable duration of participation, the safety and biomarker data from the Open-label Cohort will not be used for the primary data analysis, although a secondary analysis of these data may be used for regulatory filings.

Descriptive statistics will be presented as counts and percentages for categorical variables, counts and ranges for events, and means with standard deviations, medians, and ranges for continuous variables. For safety and tolerability measures, we will consider clinical, rather than statistical, significance. Initial determinations will be made by the independent medical safety monitor physician familiar with the study population and blinded to treatment allocation.

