For modeling and inferential tests, we will consider a p-value less than 0.1 to be significant if the magnitude and precision of the estimated effect support that conclusion. Covariates will be specified in the description below. We will perform extensive exploratory data analysis and checks of model fit and will transform variables with obvious departures from normality.

Analysis of primary endpoints

Safety Analysis

Comparisons of participants experiencing treatment-emergent adverse events and clinically-significant abnormalities on clinical labs will be reviewed for clinical significance in the Safety Analysis dataset, which includes all participants who consume at least one dose of the study product. Events expected as part of the usual disease course in PKAN, whether present at trial enrollment or not, will not be considered or captured as adverse events.

Frequencies of participants experiencing at least one adverse event (AE) will be displayed by body system and preferred term according to *Medical Dictionary for Regulatory Activities* (MedDRA) terminology. Detailed information collected for each AE will include a description of the event; duration; whether the AE meets criteria as a Serious Adverse Event (SAE); severity / grade of the event; relationship to study product; changes made to the study product in response to the AE /SAE; and clinical outcome. Severity of the AEs will be graded according to the NCI *Common Terminology Criteria for Adverse Events*, Version 4.0. If the event meets criteria as an SAE, the nature of the SAE will be classified using standard FDA criteria.

The number and percentage of patients who experienced any serious AE (SAE), treatment-emergent AE, and treatment-emergent SAE will be summarized, as well as the total number of events per arm. AE data will be presented for months 0-6 and 7-37 and cumulatively, as appropriate. Emphasis in the analyses will be placed on AEs classified as treatment-emergent.

Clinically-significant abnormalities on clinical labs will be tabulated similarly to AEs. The number and percentage of patients experiencing clinically-significant abnormalities will be compiled in summary tables to examine the distribution by collection month [0-1-3-6-7-9-12-18-24 (25) months for the Primary Cohort; and 0-1-3-6-12-18 (19) months for the Open-label Cohort].

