As a final step, we will develop a **longitudinal model to characterize CoASY mRNA expression profiles over the entire 24-month study treatment period**. We plan to use a mixed effects model with random intercept and slope to account for correlation between measurements and to allow individuals to vary from the group mean. We will explore a number of possible parameterizations of the time effect, including fractional polynomials and splines. We will allow for different trajectories by (a) dose group and (b) PKAN type in separate models with a group x time interaction. This model will take the general form $CoASY_{ij} = \beta_0 + \beta_1 t_{ij} + \beta'_2 group + \beta_3 t_{ij} \times group + b_{1i} + b_{2i} t_{ij}$, where t_{ij} represents time on treatment in months (including partial months as decimals) and group indicates dose group or PKAN type, depending on the model.

Latent growth curve modeling plan for the exploratory aim will not be described here but is described in full in the protocol.

1. Protocol Title: A phase 2 study of a vitamin metabolite in PKAN

2. Objectives

The primary objective of this study is to assess the safety and tolerability of 4'-phosphopantetheine (4'-PPT), a product of intermediary metabolism, in pantothenate kinase-associated neurodegeneration (PKAN), an inborn error of vitamin B5 metabolism. The study product meets the FDA statutory definition for consideration as a medical food and is being developed as such for the nutritional management of PKAN.

The primary hypothesis is that there will be no clinically significant difference in safety or tolerability profiles between active and placebo groups during six months of double-blind parallel study, nor between dose groups over up to 18 months of treatment with 4'-PPT.

The primary aims are:

- To compare safety or tolerability profiles of 4'-PPT between active and placebo groups over the 6-month double-blind parallel group phase of the study; and
- To examine the long-term safety and tolerability profile of the compound over up to 18 months of open-label period.

The primary endpoints are:

- Safety outcome measures will include treatment-emergent adverse events and abnormalities on standard laboratory tests collected over up to 24 months of treatment.
- Tolerability outcomes will be assessed via participant retention in the study and adherence to the study product regimen.

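### The primary claim of no clinically significant difference from placebo is to be judged from counts and percentages with no measure of precision, and about 15 placebo participants leave large differences open

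*Combined protocol and SAP*

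**What the plan says.** The Synopsis (Study Objective and Specific Aims) and protocol section 2 state the primary hypothesis as a claim of no difference: "there will be no clinically significant difference in safety or tolerability profiles between active and placebo groups during six months of double-blind parallel study".

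The Synopsis, Statistical Methods, General approach, says how it will be judged: "For safety and tolerability measures, we will consider clinical, rather than statistical, significance". It adds: "Initial determinations will be made by the independent medical safety monitor physician familiar with the study population and blinded to treatment allocation".

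The same section lists the summaries: "Descriptive statistics will be presented as counts and percentages for categorical variables, counts and ranges for events", with means, standard deviations, medians and ranges for continuous variables. For safety, "The number and percentage of patients who experienced any serious AE (SAE), treatment-emergent AE, and treatment-emergent SAE will be summarized", along with the total number of events per arm. Protocol section 10b repeats this and treats clinically significant laboratory abnormalities in the same way. Retention is compared as numbers retained in each arm. Section 10d compares adherence by means and standard deviations.

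No confidence interval, margin or other statement of precision is attached to any safety or retention comparison, in either the Synopsis or the protocol body.

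The size is "15 in each arm + 4 potential dropouts allowing for 5% loss to follow-up", and allocation is to one of three doses "or placebo in a 1:1:1:1 distribution".

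**The concern.** A hypothesis of no difference is supported only to the extent that the data rule out differences that would matter. Two similar percentages can arise because the product is as well tolerated as placebo, or because too few participants were observed to show otherwise. The planned tables do not tell the reader which applies.

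The trial's main conclusion is at stake. Protocol section 13a says the product has not been studied in humans before, and children are enrolled. If adverse event percentages look alike at 6 months, the natural sentence is that no clinically significant difference was found. Nothing in the plan requires the report to say how large a difference the data leave open.

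Declining significance tests for safety is reasonable at this size. The gap is the absence of any expression of uncertainty beside the percentages.

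**Working it through.** **Inputs from the documents.** 15 evaluable participants per arm and three active arms to one placebo arm (Synopsis, Sample Size Considerations and Study Design), so 3 × 15 = 45 pooled active against 15 placebo. The safety set is everyone who took at least one dose, so up to 64/4 = 16 per arm.

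**The plan's own figure.** 60 evaluable with 5% loss: 60/0.95 = 63.2, rounded up to 64. This reproduces. The number is set by rarity, and the only power figure (85-95%) is for the CoASY biomarker, not for safety.

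**Inputs assumed.** The documents give no adverse event rates, so observed rates of 20%, 40% and 60% are used as a range.

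**Step 1: no events observed.** The exact two-sided 95% upper limit for 0/n is 1 − 0.025^(1/n).
- n = 15: 1 − 0.025^(1/15) = 21.8% (one-sided, with 0.05: 18.1%)
- n = 16: 20.6%
- n = 45: 7.9% (one-sided: 6.4%)

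**Step 2: equal observed rates.** The Newcombe 95% interval for p₁ − p₂ uses the Wilson limits (l, u) of each proportion:
- lower = (p₁ − p₂) − √[(p₁ − l₁)² + (u₂ − p₂)²]
- upper = (p₁ − p₂) + √[(u₁ − p₁)² + (p₂ − l₂)²]

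Worked case, 9/45 against 3/15 (20% each). The Wilson limits are 0.109 to 0.338 on active and 0.070 to 0.452 on placebo.
- lower = −√[(0.200 − 0.109)² + (0.452 − 0.200)²] = −0.268
- upper = √[(0.338 − 0.200)² + (0.200 − 0.070)²] = 0.189

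| Active | Placebo | Observed rate | 95% interval, active minus placebo (points) |
|---|---|---|---|
| 9/45 | 3/15 | 20% each | −27 to +19 |
| 18/45 | 6/15 | 40% each | −28 to +25 |
| 27/45 | 9/15 | 60% each | −25 to +28 |
| 3/15 (one dose) | 3/15 | 20% each | −28 to +28 |
| 24/48 | 8/16 | 50% each | −26 to +26 |

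The upper limit is the one that bears on excess harm. The last row shows that counting 16 per arm changes little.

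**Step 3: how often a real excess would look small.** Exact binomial enumeration, 45 against 15, with a true excess of 20 points. The observed pooled difference is 5 points or less in 13% of trials if the true rates are 20% on placebo and 40% on active, and in 16% if they are 40% and 60%.

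**The case against.** The other side has real force on several points.

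- **The safety review is broader than one opinion.** A reader might infer that a single physician decides the primary question. The documents do not support that. The blinded physician makes only the initial determination. The principal investigator rules on seriousness and relatedness, and a full data safety monitoring board reviews summary reports (section 12). Events are recorded with grade, relatedness and outcome, and are listed by participant. This stands, but none of it expresses the uncertainty of a group comparison.
- **The plan does not announce a safety claim from similarity.** A reader might infer that similar percentages will be reported as evidence of safety. The nearest text, under Tolerability Analysis, says only that high retention and consumption will count as evidence of tolerability. It concerns neither safety nor similarity between arms.
- **Effect sizes are put ahead of power** in Sample Size Considerations. That favours estimation but names no precision measure for safety. Precision is mentioned again in the rule for p-values below 0.1, but that rule governs modelling and inferential tests, which are specified only for CoASY and the exploratory growth curves.
- **Size is fixed by rarity, and a reader can compute intervals from the counts.** Both are true. The defect therefore lies in presentation and interpretation, not in design or data. It is no reason to ask for a test, a margin or more participants.
- **Intervals by dose for every item would clutter the report.** This also stands: at 15 against 15 and 20% each, they span about 28 points either way.

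**Conclusion.** The point holds as one about precision and interpretation. The plan states a primary hypothesis of no clinically significant difference but provides nothing to show what the active versus placebo comparison can exclude. With about 15-16 placebo participants, equal observed rates between 20% and 60% would still be compatible with an excess on active of about 19 to 28 points. An event unseen in 15 participants could have a true rate up to 22%, and one unseen in 45 up to 8%.

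The event rates are assumptions, and the intervals assume 45 against 15 evaluable participants. The imprecision of the difference comes mainly from the placebo arm; for events absent on placebo, the 45 active participants are more informative. The finding concerns the 6-month comparison with placebo. It does not show that the planned safety monitoring is inadequate or that descriptive safety analysis is wrong in an ultra-rare disease. It is a worthwhile, inexpensive improvement because it changes what the trial may conclude.

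**What to change.** Keep the clinical review as planned. In the Synopsis, Statistical Methods, and in protocol section 10b, add the following for months 0-6:

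1. An exact 95% confidence interval for the percentage of participants with any treatment-emergent adverse event, any serious adverse event and any clinically significant laboratory abnormality, and for the percentage retained.
2. A 95% confidence interval (for example Newcombe) for each corresponding risk difference, pooled active minus placebo. Differences for each dose may be shown as supportive.
3. A sentence stating that the primary conclusion will be expressed as the size of difference the data do and do not exclude, and that similar percentages alone will not be taken to show no difference.

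The cost is a few table columns and a more modest conclusion. No test, margin, extra data or change in sample size is needed.
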